Carry Life® UF treatments: 10 ml dialysate samples at 0, 1, 2, 3, 4 and 5 hours will be analyzed for dialysate glucose and sodium for evaluation of dialysate glucose and sodium concentrations during treatment. All PD fluid automatically drained (and any additional drains) during the Carry Life® UF treatment will be pooled. The pooled PD fluid, plus the final peritoneal drain will be analyzed for dialysate glucose, sodium, potassium, calcium, phosphate, albumin, creatinine, and urea for calculation of glucose ultrafiltration (UF) efficiency, glucose absorption and peritoneal removal of the listed substances.

**Home phase efficacy evaluation days, during week 2 and week 4 or each arm:** Drained dialysate from the control and Carry Life® UF efficacy evaluation treatments (Carry Life® UF drain bag + final peritoneal drain) will be collected by a research assistant for analysis of dialysate glucose, sodium, potassium, calcium, phosphate, albumin, creatinine, and urea, for calculation of glucose absorption, glucose UF efficiency, and peritoneal removal of the listed substances.

j. **In-clinic phase:** The volume and glucose concentration of PD bags used for the PET and Carry Life® UF treatments will be recorded.

**Home treatment phase:** The subjects will record information of all PD bags used (volume and glucose concentration for glucose-based solutions and volume for icodextrin).

k. **In-clinic phase:** The PD bag and glucose bag will be weighed by a clinical professional before the treatment and the drain bag(s) will be weighed after the treatments for calculations of fill volume, drained volume and UF volume.

**Home treatment phase:** Subject will record fill and drain weights of all dwells every day during the home phase.

**Home treatment phase efficacy evaluation days:** A research assistant will weigh the solution bags (PD bag and glucose bag), and the drain bags for calculations of fill volume, drained volume and UF volume.

l. 24-hour urine volume and urine concentration of creatinine and urea will be collected for calculation of residual renal function.

m. The patient will weigh the PD bag, glucose bag and drain bag(s) for each CAPD dwell/Carry Life® UF treatment during the home phase of the study for evaluation of weekly UF volume.

n. To assess the Carry Life® UF safety at the different glucose doses, each in-clinic Carry Life® UF treatment will be evaluated for the following:

1) a systolic blood pressure of < 100 mmHg.

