**Table 7. The tests methods, recording and analysis of variables**

Test/assessment	Required measurements	Recording	Analysis	Source data
PD fill volume	Weight of full PD bags with or without outer wraps. Weight of plastic material (may be predetermined).	In-clinic visits, PET, and Carry Life® UF treatments: Home phase efficacy evaluations treatments (control and Carry Life® UF).	Calculated by electronic data capture (EDC): The weight of full PD bags minus weight of the plastic material.	Work sheets for measured data and eCRF for calculated data.
Drained volume	Weight of drain bags. Weight of plastic material (may be predetermined)	All CAPD dwells and Carry Life® UF treatments during home phase.	Calculated by EDC: The sum of all volumes drained for each treatment, including all dialysate sample volumes.  The drained volume in each drain bag is calculated as the weight of the drain bag minus the weight of the plastic material.	Work sheets for measured data and eCRF for calculated data.
Treatment time (hours)	Time for end of peritoneal fill and start of peritoneal drain.		Calculated by EDC: Time between "end of peritoneal fill" and "start of peritoneal drain"	Work sheets for measured data and eCRF for calculated data.
Glucose volumeexact	Weight of full glucose bag with or without outer wrap. Weight of used glucose bag. Weight of plastic material (may be predetermined)	Carry Life® UF in-clinic treatments and Carry Life® UF efficacy evaluation treatments (ml).	Calculated by EDC; Weight of full glucose bag minus weight of used glucose bag (g) divided by the density of the 50% glucose solution (1.2235 g/ml).	Work sheets for measured data and eCRF for calculated data.
Glucose volumeapprox for Carry Life® UF home treatments other than efficacy evaluation days (ml)	None, nominal volume for the 5 hour Carry Life® UF treatment at each dose 110 ml (11 g/h) and 150 ml (15 g/h) is used.	Daily during Carry Life® UF arm	N/A	eCRF (prescribed Carry Life UF glucose dose).

Test/assessment	Required measurements	Recording	Analysis	Source data
UF volumeexact (ml)	PD fill volume. Glucose volume. Drained volume.	In-clinic visits, Home phase efficacy evaluations treatments	Calculated by EDC; Drained volume-PD fill volume - Glucose volume exact .	Work sheets for measured data and eCRF for calculated data.

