UF volumeapprox. (ml)	PD fill volume. Glucose volume. Drained volume.	All dwells/Carry Life® UF treatments during home phase.	Calculated by EDC; Drained volume-PD fill volume - Glucose volume approx.	Work sheets/electronic patient-reported outcome measures (ePROM) for measured data and eCRF for calculated data.
UF rate (ml/kg body weight/treatment)	UF volume exact . Body weight before treatment.	In-clinic phase, Carry Life® UF treatments.	Calculated by EDC; UF volume exact /Body weight before treatment.	Work sheets for measured data and eCRF for calculated data.
UF volume % increase	UF volume exact	End of In-clinic phase	Calculated by EDC; ([UF volume exact Visit4/ UF volume exact Visit3]-1)*100	eCRF
Dose determination	UF volume % increase	End of In-clinic phase	Determined by EDC according to dose determination algorithm.	
Dialysate glucose concentration	Glucose concentration in drain samples	In-clinic phase, PET, and Carry Life® UF treatments: PET: T0, T1h, T2h, T4h Carry Life UF: T0, T1h, T2h, T3h, T4h, T5h, peritoneal drain	Laboratory analysis	Laboratory data
Peak dialysate glucose concentration	Glucose concentration in drain samples	In-clinic phase, Carry Life® UF treatments: T1h, T2h, T3h, T4h, T5h	Data analysis	N/A
PET	Sodium and creatinine concentration in dialysate.	PET, at T0, T1 and T2 T4	D/P creatinine  Transfer type determined as D/P creatinine at 4h Low: 0.34-0.50 Low average: 0.50-0.65 High average: 0.65-0.81 High: 0.81-1.03  Sodium dip: Dialysate sodium: T1 minus T0	Laboratory data

Test/assessment	Required measurements	Recording	Analysis	Source data
Glucose absorption	PD fill volume. Glucose volume exact . Drain volumes (peritoneal drain + Carry life UF drain bag). Glucose concentration of drain volumes (peritoneal drain + Carry life UF drain bag).	In-clinic (Carry Life UF treatments) Home phase efficacy evaluations treatments (control and Carry Life® UF).	Sum of glucose added (PD fill volume (ml) * glucose concentration of PD solution (13.6 or 22.6 g/ml) + Glucose volume exact (ml) * 0.5 g/ml) minus the sum of glucose drained (peritoneal drain volumes * the glucose concentration of drain volumes (g/ml)).	Work sheets for measured data, laboratory data and eCRF for calculated data.

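### On home days other than evaluation days, Table 7 subtracts a nominal glucose volume although Table 1 footnote m has the glucose bag weighed, so exploratory weekly UF is understated when less is delivered

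*Protocol*

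**What the plan says.** Table 7 (section 6.2.8) defines two glucose volumes and two UF volumes.

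- The exact glucose volume comes from weighing the bag full and used. Its scope is "Carry Life® UF in-clinic treatments and Carry Life® UF efficacy evaluation treatments (ml", and it enters the exact UF volume as "Drained volume-PD fill volume - Glucose volume exact".
- The approximate glucose volume applies to "home treatments other than efficacy evaluation days (ml". The required measurement is given as none, the value is the "nominal volume for the 5 hour Carry Life® UF treatment at each dose 110 ml (11 g/h) and 150 ml (15 g/h", and the source is "eCRF (prescribed Carry Life UF glucose dose". It enters the approximate UF volume as "Drained volume-PD fill volume - Glucose volume approx".

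Footnote m to Table 1 says something different about the same home treatments: "The patient will weigh the PD bag, glucose bag and drain bag(s) for each CAPD dwell/Carry Life® UF treatment during the home phase". Its stated purpose is "for evaluation of weekly UF volume". Footnote k asks the subject for daily fill and drain weights and does not name the glucose bag on ordinary home days. Table 5 lists weighing the solution bags before treatment, but only the drain bags afterwards. Section 8.1 has subjects record solution weights daily without saying which ones.

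**The concern.** The protocol fixes both the measurement and the formula, and they disagree, so this cannot simply be left to the SAP. A site following footnote m collects a glucose weight that Table 7 never uses. A site following Table 7 does not collect it.

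The nominal figure reflects the prescribed dose, not the delivered one. Section 14.4.3 says patients can always end a treatment and describes alarms they cannot resolve. Section 7.1.4 limits treatment time and total stop time for per protocol treatments, but Table 7 applies the approximate UF volume to all home treatments, so those limits do not screen the diary data.

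Weekly UF is an exploratory endpoint compared across arms (section 7.1.8). CAPD dwells have no added-glucose term, so an error in that term enters the device arm only. Where delivery falls short, it works against the device, and it is largest in subjects whose treatments end early.

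**Working it through.** Inputs:

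- Glucose doses of 11 and 15 g/h over 5 h (section 2.6 and Table 7).
- Solution concentration 0.5 g/ml and density 1.2235 g/ml (section 8.1).
- About 12 home device treatments per subject (section 6.2.10), two of them on evaluation days (section 6.1), which leaves about 12 − 2 = 10 on the nominal volume.
- Automatic stop at 5 h, with up to 15 min run-on (section 6.2.6); at most 30 min stop time in a per protocol treatment (section 7.1.4).
- 750 ml per week as the sponsor's clinically relevant gain (section 7.1.1), used here for scale only.

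**1. Reproduce the nominal volumes.** Dose × 5 h ÷ 0.5 g/ml: 11 × 5 / 0.5 = 110 ml and 15 × 5 / 0.5 = 150 ml. Both agree with Table 7. Per hour: 110 / 5 = 22 ml and 150 / 5 = 30 ml.

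**2. Error in the approximate UF volume.** With D drained, F filled and V the glucose volume, (D − F − V nominal) − (D − F − V delivered) = V delivered − V nominal. A shortfall lowers the calculated UF by exactly the undelivered volume.

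**3. Size, assuming delivery proportional to time.** Understatement = hourly volume × dosing hours lost.

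| Case | Hours lost | 11 g/h | 15 g/h |
|---|---|---|---|
| 30 min lost | 0.5 | 11 ml | 15 ml |
| Stopped at 4.25 h | 0.75 | 16.5 ml | 22.5 ml |
| 1 h lost | 1 | 22 ml | 30 ml |
| Stopped at 2 h | 3 | 66 ml | 90 ml |
| Stopped at 1 h | 4 | 88 ml | 120 ml |

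**4. Weekly scale.** If all three treatments in a week each lost 30 min of dosing: 3 × 11 = 33 ml or 3 × 15 = 45 ml. Against 750 ml these are 33 / 750 = 4.4% and 45 / 750 = 6.0%.

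**5. Opposite direction.** If dosing continued through a full 15-minute run-on (an assumption), UF would be overstated by 22 × 0.25 = 5.5 ml or 30 × 0.25 = 7.5 ml.

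**6. What weighing would show.** A full nominal dose weighs 110 × 1.2235 = 134.6 g or 150 × 1.2235 = 183.5 g. A 30-minute loss is 11 × 1.2235 = 13.5 g or 15 × 1.2235 = 18.4 g; a stop at 2 h is 66 × 1.2235 = 80.8 g or 90 × 1.2235 = 110.1 g. The protocol does not state the resolution of the home scales, so small losses may sit close to weighing error.

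**The case against.** The best defence is that the approximation is deliberate. Table 7 separates exact from approximate quantities and gives the cruder one to unsupervised treatments that feed an exploratory comparison described only as basic. The nominal figures are right for a full treatment, and the error at the 30-minute limit is 11 or 15 ml. All of that stands and keeps the point minor. It does not explain why footnote m asks for a weight, for the same endpoint, that the formula ignores.

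Four stronger readings are tempting, and the protocol does not support them.

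- *Every interrupted treatment gets too low a UF.* Section 2.6 describes dosing in 13.5-minute cycles, with the pump idle once the cycle's volume is given. A short halt may lose no dose, and the protocol does not say whether missed dosing is made up.
- *The error can go only one way.* The permitted run-on could produce a small overstatement.
- *The glucose volume is the only device-specific input to weekly UF.* The device also drains about 180 ml each hour, and the drained volume is measured and enters the formula.
- *Footnote m already supplies the delivered volume.* It does not say that the used bag is weighed, and a delivered volume needs weights before and after.

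Nor does the protocol indicate how often treatments will stop at 1 or 2 h, so the larger figures show what one such treatment would cost, not what to expect.

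**Conclusion.** The conflict between Table 7 and footnotes k and m is real. For home device treatments off the evaluation days, about 10 per subject, the calculated UF is too low by whatever glucose solution was not delivered: 22 or 30 ml per lost hour of dosing if delivery is proportional to time. The effect is confined to the device arm of the exploratory weekly UF.

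A reader might infer that the trial's main result is at risk. It is not: the primary endpoint, sodium removal and glucose UF efficiency all come from the efficacy evaluation treatments (sections 7.1.6, 7.1.7.2 and 7.1.7.3), where Table 7 uses weighed glucose. The point is worth correcting because the correction is cheap and builds on a weighing that footnote m already requests, not because the expected bias is large.

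**What to change.** Reconcile Table 7 with Table 1 footnotes k and m so that all three state the same rule.

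- Record the glucose bag weight before and after each home device treatment, and name both weights in footnotes k and m.
- In Table 7, replace the nominal volume in the approximate UF volume with (weight before − weight after) ÷ 1.2235 g/ml.
- Where a weight is missing, use 22 or 30 ml per hour times the recorded device running time. Do not use Table 7's treatment time for this: it runs from end of fill to start of drain and so includes connection and priming. Device running time therefore needs its own diary field.

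The cost is one additional bag weighing after each home treatment, the matching diary and eCRF fields, and one changed formula. Sites that followed Table 7 and weighed no glucose bag would also have to add the weighing before treatment. If the sponsor judges the extra weighing too burdensome for an exploratory endpoint, the alternative is to remove the glucose bag from footnote m and scale the nominal volume by recorded running time. That still leaves the proportional-delivery assumption untested.

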During the home treatment phase subjects will record clinical measurements and solution weights daily. Primarily, the subjects will enter the data (e.g., weight and blood pressure) into a mobile application. The data entered into the App will be transferred directly into the eCRF and there is no additional source documentation expected and thus these values are not subject to source data verification through the monitor. In case a subject does not use the App, but records data in a paper-based diary instead, the data are entered by dedicated site staff into eCRF and are subject for source data verification. However, in case of out of limit measurements the site is going to be alerted by means of a query and is going to follow-up with the patient to verify and discuss the entered data for any potential error. When copies of original source documents as well as printouts of original electronic source documents are retained, these shall be signed and dated by a member of the investigation site team with a statement that it is a true reproduction of the original source document. Copies of the source data shall remain at the clinical investigation site when the investigation is completed allowing an independent account of the investigation process.

The data from the eCRF will be managed in an EDC system. The EDC database will be programmed to use the input data from the eCRF to calculate output data including the endpoint measures (e.g., UF volume, peritoneal removal of the substances analyzed in the dialysate, and glucose efficiency). To be able to perform the calculation the following constants will be used:

- Glucose molecular weight: 180.16 g/mol.
- 50% glucose solution concentration: 0.5 g/ml.
- Density 50% glucose solution: 1.2235 g/ml.

Additionally plastic weights of solution bags and drain bags may be pre-weighed and used to calculate fill and drain volumes.

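### The primary UF formula subtracts millilitres of glucose solution from grams of fill and drain, so on a volume basis the device-control difference is overstated by roughly 20-23 ml against a 250 ml margin

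*Protocol*

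**What the plan says.** Section 6.2.8, Table 7 of the protocol defines the components of UF as follows.

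- **PD fill volume:** "The weight of full PD bags minus weight of the plastic material", which is a weight in grams.
- **Drained volume, per bag:** "calculated as the weight of the drain bag minus the weight of the plastic material", again grams.
- **Glucose volume exact:** bag weight used, "divided by the density of the 50% glucose solution (1.2235 g/ml"), which is millilitres.
- **UF volume exact:** "Drained volume-PD fill volume" less glucose volume exact, labelled ml.
- **UF volume approx** has the same structure, but for the glucose term the "nominal volume for the 5 hour Carry Life® UF treatment at each dose 110 ml (11 g/h) and 150 ml (15 g/h) is used".

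Section 8.1 lists the constants programmed into the EDC. The only density is "Density 50% glucose solution: 1.2235 g/ml". None is given for PD solution or for drained dialysate.

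UF volume exact supplies the primary endpoint from the home efficacy treatments, tested against a 250 ml superiority margin (sections 5.2 and 7.1.6). It is also the UF term in glucose UF efficiency, and it feeds the in-clinic UF rate and the dose determination (Table 7, section 6.2.2). UF volume approx is calculated for all home dwells, which are the source for weekly UF.

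**The concern.** Two terms of the subtraction are in grams and the third is in millilitres. For fluids close to 1 g/ml this would hardly matter, but the glucose solution weighs 1.2235 g/ml. Its weight enters the peritoneal cavity and, apart from what is absorbed, is weighed again in the drain bags, while only its smaller millilitre figure is taken off.

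The control dwell has no glucose-solution term, so pairing and crossover cannot cancel the discrepancy. It shifts the primary contrast in the device's favour, and a larger sample does not shrink it. Because the test is against a fixed margin, a constant shift raises the chance of declaring superiority when the true difference sits at the margin. Section 6.4.3 itself stresses exact determination of the instilled and drained volumes, and section 6.2.6 discusses a treatment-time bias said to favour control. This bias runs the other way and is not mentioned.

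**Working it through.** **1. Reproduce the protocol's nominal volumes.** Dose x 5 h / 0.5 g/ml (section 8.1): 11 x 5 / 0.5 = 110 ml and 15 x 5 / 0.5 = 150 ml. Both agree with Table 7.

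**2. Gap to all-gram accounting.**
- 110 ml x 1.2235 = 134.6 g; 134.6 - 110 = 24.6.
- 150 ml x 1.2235 = 183.5 g; 183.5 - 150 = 33.5.

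This uses only the protocol's constants. It compares the formula with the convention 1 g = 1 ml throughout, not with a true volume.

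**3. Error on a true volume scale.** Assume water at 1 g/ml, and that a fluid's grams exceed its millilitres by k per gram of dissolved glucose. Other solutes and temperature are ignored. From the 50% solution, k = (1.2235 - 1) / 0.5 = 0.447. The glucose brought in with the fill appears in both fill and drain and cancels, which leaves:
- device error = k x (glucose infused by the device - glucose absorbed);
- control error = -k x glucose absorbed.

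Absorption is taken from the Tmed-007 means in section 3.8 as UF / glucose UF efficiency:
- control 162 / 5.9 = 27.5 g;
- 11 g/h: 646 / 17.0 = 38.0 g;
- 14 g/h: 739 / 14.5 = 51.0 g, standing in for 15 g/h.

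| | Infused (g) | Device error (ml) | Control error (ml) | Difference overstated by (ml) |
|---|---|---|---|---|
| 11 g/h | 55 | 0.447 x (55 - 38.0) = +7.6 | -0.447 x 27.5 = -12.3 | 19.9 |
| 15 g/h | 75 | 0.447 x (75 - 51.0) = +10.7 | -12.3 | 23.0 |

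**4. Range.**
- If a gram of glucose is assumed to occupy up to 0.65 ml (k = 0.35) rather than the 0.553 ml implied above, the difference is overstated by 15.6 ml (11 g/h) or 18.0 ml (15 g/h).
- A second route to absorption uses device dialysate at 1.6% and 1.9% (section 4.1) and 32 g absorbed from a 2 L 2.27% dwell (Table 4). Device: 27.2 + 55 - 2756 x 0.016 = 38.1 g and 27.2 + 75 - 2889 x 0.019 = 47.3 g, giving errors of +7.6 and +12.4 ml. Control: -0.447 x 32 = -14.3 ml. Net: 21.9 and 26.7 ml.

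The overall range is roughly 16-27 ml: 16 / 250 = 6% to 27 / 250 = 11% of the margin.

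**5. Effect on the test.** One-sample one-sided t-test, alpha 0.025, n = 19, true difference exactly 250 ml; noncentral t with noncentrality bias / (SD / sqrt 19).

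| Bias (ml) | SD 330 | SD 236 |
|---|---|---|
| 0 | 2.5% | 2.5% |
| 16 | 3.9% | 4.7% |
| 20 | 4.4% | 5.4% |
| 23 | 4.7% | 6.0% |
| 27 | 5.2% | 6.9% |

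**6. At the pilot difference.** 574 - 27 = 547 ml; (547 - 250) / (236 / sqrt 19) = 5.5 standard errors above the margin. The conclusion is unaffected.

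**The case against.** The strongest objection is that the effect is small and its size uncertain. It is at most about a tenth of the margin. The error rates apply only if the truth lies exactly at 250 ml, whereas the protocol plans on 400 ml conservatively and saw 574 ml in the pilot. The magnitude depends on drained-dialysate density, which the protocol does not give, on absorption taken as a ratio of means, and on 14 g/h standing in for 15 g/h. The pilot control dwell also lasted 4 hours, not 5. The weighing procedures in Attachments E and F appear only as titles. All of this limits the precision of the estimate. It does not remove the unit mismatch, and nothing in the text at hand suggests that the attachments override Table 7.

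A reader might also infer from step 2 that device UF is overstated by 25-34 ml, with error rates up to 6.2% (SD 330) or 8.5% (SD 236). The documents do not support that. The protocol's own pilot figures imply 38-51 g of glucose absorbed per device treatment, and this mass never reaches the drain bag. On a volume scale the device error is about 8-11 ml. The larger share of the between-arm bias, about 12 ml, is control UF being understated, because weights are read as millilitres while glucose is being absorbed. The density division alone does not produce that part.

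**Conclusion.** The formula for the primary endpoint is inconsistent as written, and the inconsistency favours the device. The best estimate is that the device-control difference is overstated by about 20-23 ml (roughly 16-27 ml across assumptions), or 6-11% of the 250 ml margin. At a true difference of 250 ml with n = 19, the one-sided error becomes about 4-5% (SD 330) or 5-7% (SD 236) instead of 2.5%.

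Confidence is high on the mixed units and the direction, and moderate on the size, which rests on pilot mean absorption, water at 1 g/ml and excess density due to glucose alone. The point should be corrected because the margin is fixed and the correction is cheap. It would not overturn a result near the pilot difference.

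**What to change.** In Table 7 and the EDC, put all terms of UF volume exact and UF volume approx on one stated basis. There are two options.

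- **All volumes:** divide every weight by its own stated density (PD solution, drained dialysate, 50% glucose solution). This is the fuller correction, but the first two densities must be added to the protocol.
- **All weights:** drained g minus fill g minus glucose solution g, reading 1 g of UF as 1 ml. For UF approx, subtract 134.6 g or 183.5 g in place of 110 or 150 ml. This needs only weights already recorded. It is not exact: under the main assumptions in step 3 it leaves the difference about 5-11 ml too low (19.9 - 24.6 = -4.7; 23.0 - 33.5 = -10.5). That error is smaller than the present one and is conservative. The protocol should say so.

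Keep 1.2235 g/ml for computing the grams of glucose delivered.

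**Cost:** the weight option is a one-line change to each formula, with no new visits or samples. The observed UF difference becomes slightly smaller. UF volume exact also feeds the in-clinic UF rate and dose determination, so the thresholds in section 6.2.2 and the corresponding rows of Table 7 must be reconciled with the revised formula. How they are reconciled is a clinical decision for the sponsor and investigators.
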